| Treatment 
 - eCR (30% calorie restriction, 8am – 4pm); - dCR (30% calorie restriction, 12pm – 8pm); - CR (30% calorie restriction, 8am-8pm); Control group | |
| ESTIMAND | ANALYSIS |
| Target population 
 - Men and women with obesity and elevated fasting blood glucose | Analysis set 
 - All randomized - Initiated diet |
| Variable 
 - Glucose AUC over 3 meals (breakfast, lunch, dinner). | Outcome measure 
 - Blood glucose AUC - Measured at 0,30,60,120 post-meal - Averaged over three meals |
| Handling of inter-current events 
 1. Death (while on treatment strategy, or “while alive”) 2. Discontinuation: other reason (while on treatment strategy) 3. Discontinuation: dislike of diet (treatment policy strategy) 4. Lost-to-follow-up no reason provided (treatment policy strategy) | Handling of missing data 
 1. Death believed not to be relevant for this study, included for completeness. 2. All individuals discontinuing early will (i) be invited to attend the week 6 assessment for fasting bloods and body weight only, (ii) asked whether the reason for discontinuation is due to allocated diet. 3. Missing-at-random will be assumed for individuals who do not specify whether discontinuation was due to diet, or when the reason was not due to the diet. 4. For individuals who discontinued due to the diet a missing-not-at-random assumption will be made, assuming zero adherence after discontinuation, and conditional on adherence missing-at-random assumed to impute week 8 outcomes. |

| | |
|---|--|
| | 5. Imputation is by treatment group with individuals imputed in the groups they were allocated to. |
| Population level summary measure 
 - Mean between group differences in baseline adjusted log-transformed (within-individual) mean post-meal glucose AUC, of the time-restricted groups versus the control (non time-restricted) group. | Analysis approach 
 - Group differences of log transformed mean post-prandial AUC will be estimated using a single linear regression with a treatment (three levels) and baseline log transformed mean post-prandial glucose AUC and stratification factors (sex and fasting plasma glucose). |

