A secondary, complete-case sensitivity analysis will be performed for the analysis of the primary outcome and secondary efficacy outcomes in this analysis individuals with both baseline and week 8 assessments will only be included for each analysis.

As additional analysis will explore the treatment effects within subjects who were adherent to the protocol using data collected with the MyCircadianClock app plus the dietary checklists. This analysis will be reported in a secondary mechanistic publication of this study.

STATISTICAL METHODS

Primary Outcome

The primary analysis of the primary outcome is a covariate adjusted linear regression of the differences in PP glucose log AUC at 8 weeks from baseline. Covariates included will be treatment (three groups), baseline glucose log AUC, sex and fasting plasma blood glucose (as a continuous linear variable). Visual inspection of the residual distribution will be used to determine if assumptions of normality and the absence of a variance-mean association appear to be violated. If assumptions appear violated a generalized linear models will be considered with differing link functions will be considered and presented as sensitivity analyses. Given the limited sample size, no subgroup analyses are planned.

This analysis will be performed in all randomized individuals with individuals using multiple imputation using chained equations within treatment groups and combined using Rubin's rules. The variables used in the multiple imputation are age and sex; baseline and week 8 assessments of weight, PP glucose and insulin AUC (per meal), fasting glucose, fasting insulin and HbA1c; and the self-reported adherence over the 8 weeks and reason for discontinuation (related/unrelated to diet) if applicable. All concentrations will be imputed on the log scale, with the 3-meal mean of PP glucose and insulin AUC being calculated on the original scale after a back-transformation. Compliance will be imputed as per the intercurrent event strategies and the average compliance calculated over each period. Imputation will use multiple chained equations (*mice* R package), details of which are attached separately (file: *OMIT – Imputation code 2024-12-18.r*).

Secondary Efficacy Outcomes

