The four secondary efficacy outcomes used in the multiple imputation of the primary outcome will be assessed using the same methodology as for the primary outcome, i.e. covariate adjusted linear regressions with multiple imputation for missing data.

Exploratory Outcomes

Exploratory outcomes will also be analysed using baseline and stratification factor adjusted linear regressions. The weight and PP glucose and insulin meal specific analyses will be performed in the imputed data sets. All other outcomes will be analysed using complete case data sets.

Safety Outcomes

Summaries, for all adverse events and for those events believed to be related to the intervention, will be reported. In both cases, if an individual has experienced the adverse event on multiple occasions, only the event with the maximum grade will be reported.

When there are at least four individuals who experience a particular adverse event, a Fisher exact test will be conducted comparing the rates of occurrence (irrespective of grade) between the two intervention groups. No adjustments for multiple testing will be performed.

[figure not shown]
STUDY SUMMARY TABLES

Descriptive Statistics: A CONSORT flow chart will present all individuals screened through to randomization and week 8 assessment will be presented (Figure 2). The number of individuals who discontinue their allocated intervention and/or withdraw from the study, the week and reason for discontinuation will be reported.

Descriptive summary statistics will be reported for baseline characteristics of all individuals who were randomized. In addition to baseline glycemia indices we will report on age, sex, menopausal status, AUSDRISK, body composition, markers of CVD risk, sleep, activity and appetite measures. For continuous variables means, standard deviations, medians and ranges will be reported, and for discrete variables frequency and percentages will be reported. No demographic summary statistics were collected for the screened cohort.

Results tables presenting the analyses of the primary, secondary and exploratory outcomes are presented in Appendix A.

Figure 2: CONSORT flow chart of OMIT study.

REFERENCES

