Table A4: Exploratory outcome analyses for outcomes used in the multiple imputation of the primary outcome, ie using the imputed data.

| | A: Est [95% CI] | B: Est [95% CI] | C: Est [95% CI] | AvC: Est [95% CI] | AvC p-value | BvC: Est [95% CI] | BvC p-value |
|---------------------------|------------------------|------------------------|------------------------|--------------------------|--------------------|--------------------------|--------------------|
| Glucose.auc.break | NA [NA; NA] | NA [NA; NA] | NA [NA; NA] | NA [NA; NA] | NA | NA [NA; NA] | NA |
| Glucose.auc.lunch | NA [NA; NA] | NA [NA; NA] | NA [NA; NA] | NA [NA; NA] | NA | NA [NA; NA] | NA |
| Glucose.auc.dinner | NA [NA; NA] | NA [NA; NA] | NA [NA; NA] | NA [NA; NA] | NA | NA [NA; NA] | NA |
| Insulin.auc.break | NA [NA; NA] | NA [NA; NA] | NA [NA; NA] | NA [NA; NA] | NA | NA [NA; NA] | NA |
| Insulin.auc.lunch | NA [NA; NA] | NA [NA; NA] | NA [NA; NA] | NA [NA; NA] | NA | NA [NA; NA] | NA |
| Insulin.auc.dinner | NA [NA; NA] | NA [NA; NA] | NA [NA; NA] | NA [NA; NA] | NA | NA [NA; NA] | NA |
| Weight | NA [NA; NA] | NA [NA; NA] | NA [NA; NA] | NA [NA; NA] | NA | NA [NA; NA] | NA |

Table A5: Exploratory outcome analyses for outcomes not used in the multiple imputation of the primary outcome, ie complete case analyses.

| | A: Est [95% CI] | B: Est [95% CI] | C: Est [95% CI] | AvC: Est [95% CI] | AvC p-value | BvC: Est [95% CI] | BvC p-value |
|----------------------------------|------------------------|------------------------|------------------------|--------------------------|--------------------|--------------------------|--------------------|
| Mean Glucose CGM | NA [NA; NA] | NA [NA; NA] | NA [NA; NA] | NA [NA; NA] | NA | NA [NA; NA] | NA |
| iAUC glucose CGM | NA [NA; NA] | NA [NA; NA] | NA [NA; NA] | NA [NA; NA] | NA | NA [NA; NA] | NA |
| Nocturnal glucose CGM | NA [NA; NA] | NA [NA; NA] | NA [NA; NA] | NA [NA; NA] | NA | NA [NA; NA] | NA |
| CGM time below range | NA [NA; NA] | NA [NA; NA] | NA [NA; NA] | NA [NA; NA] | NA | NA [NA; NA] | NA |
| CGM time in range | NA [NA; NA] | NA [NA; NA] | NA [NA; NA] | NA [NA; NA] | NA | NA [NA; NA] | NA |
| CGM time above range | NA [NA; NA] | NA [NA; NA] | NA [NA; NA] | NA [NA; NA] | NA | NA [NA; NA] | NA |
| MAGE | NA [NA; NA] | NA [NA; NA] | NA [NA; NA] | NA [NA; NA] | NA | NA [NA; NA] | NA |
| MODD | NA [NA; NA] | NA [NA; NA] | NA [NA; NA] | NA [NA; NA] | NA | NA [NA; NA] | NA |

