| Insulin secretion rate | NA [NA; NA] | NA [NA; NA] | NA [NA; NA] | NA [NA; NA] | NA | NA [NA; NA] | NA |
| Insulin sensitivity index | NA [NA; NA] | NA [NA; NA] | NA [NA; NA] | NA [NA; NA] | NA | NA [NA; NA] | NA |
| HOMA-IR | NA [NA; NA] | NA [NA; NA] | NA [NA; NA] | NA [NA; NA] | NA | NA [NA; NA] | NA |
| Fasting C-peptide | NA [NA; NA] | NA [NA; NA] | NA [NA; NA] | NA [NA; NA] | NA | NA [NA; NA] | NA |
| Fasting Triglycerides | NA [NA; NA] | NA [NA; NA] | NA [NA; NA] | NA [NA; NA] | NA | NA [NA; NA] | NA |
| Fasting free fatty acids | NA [NA; NA] | NA [NA; NA] | NA [NA; NA] | NA [NA; NA] | NA | NA [NA; NA] | NA |
| Trigs AUC of 3 meals | NA [NA; NA] | NA [NA; NA] | NA [NA; NA] | NA [NA; NA] | NA | NA [NA; NA] | NA |
| Trigs AUC of breakfast | NA [NA; NA] | NA [NA; NA] | NA [NA; NA] | NA [NA; NA] | NA | NA [NA; NA] | NA |
| Trigs AUC of lunch | NA [NA; NA] | NA [NA; NA] | NA [NA; NA] | NA [NA; NA] | NA | NA [NA; NA] | NA |
| Trigs AUC of dinner | NA [NA; NA] | NA [NA; NA] | NA [NA; NA] | NA [NA; NA] | NA | NA [NA; NA] | NA |
| FFA AUC of 3 meals | NA [NA; NA] | NA [NA; NA] | NA [NA; NA] | NA [NA; NA] | NA | NA [NA; NA] | NA |
| FFA AUC of breakfast | NA [NA; NA] | NA [NA; NA] | NA [NA; NA] | NA [NA; NA] | NA | NA [NA; NA] | NA |

| | | | | | | | |
|-------------------------------|-------------|-------------|-------------|-------------|----|-------------|----|
| FFA AUC of lunch | NA [NA; NA] | NA [NA; NA] | NA [NA; NA] | NA [NA; NA] | NA | NA [NA; NA] | NA |
| FFA AUC of dinner | NA [NA; NA] | NA [NA; NA] | NA [NA; NA] | NA [NA; NA] | NA | NA [NA; NA] | NA |
| Systolic BP | NA [NA; NA] | NA [NA; NA] | NA [NA; NA] | NA [NA; NA] | NA | NA [NA; NA] | NA |
| Diastolic BP | NA [NA; NA] | NA [NA; NA] | NA [NA; NA] | NA [NA; NA] | NA | NA [NA; NA] | NA |
| Total cholesterol | NA [NA; NA] | NA [NA; NA] | NA [NA; NA] | NA [NA; NA] | NA | NA [NA; NA] | NA |
| HDL | NA [NA; NA] | NA [NA; NA] | NA [NA; NA] | NA [NA; NA] | NA | NA [NA; NA] | NA |
| LDL | NA [NA; NA] | NA [NA; NA] | NA [NA; NA] | NA [NA; NA] | NA | NA [NA; NA] | NA |
| C-reactive protein | NA [NA; NA] | NA [NA; NA] | NA [NA; NA] | NA [NA; NA] | NA | NA [NA; NA] | NA |
| BMI | NA [NA; NA] | NA [NA; NA] | NA [NA; NA] | NA [NA; NA] | NA | NA [NA; NA] | NA |
| Sleep duration | NA [NA; NA] | NA [NA; NA] | NA [NA; NA] | NA [NA; NA] | NA | NA [NA; NA] | NA |
| Arousals | NA [NA; NA] | NA [NA; NA] | NA [NA; NA] | NA [NA; NA] | NA | NA [NA; NA] | NA |

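### BMI and HOMA-IR go to complete-case analysis although weight, fasting glucose and fasting insulin, from which they are computed, are multiply imputed and analysed in all randomised participants

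*SAP*

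**What the plan says.** SAP, Primary Outcome: the analysis covers all randomised individuals, with multiple imputation within treatment groups. The imputed variables include "baseline and week 8 assessments of weight, PP glucose and insulin AUC (per meal), fasting glucose, fasting insulin and HbA1c". The same paragraph computes the three-meal mean AUC from the imputed single meals, and the R code does this for glucose and insulin at both visits.

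SAP, Secondary Efficacy Outcomes: fasting glucose and fasting insulin are analysed by "covariate adjusted linear regressions with multiple imputation for missing data" and reported in Table A1.

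SAP, Exploratory Outcomes: "The weight and PP glucose and insulin meal specific analyses will be performed in the imputed data sets". The next sentence reads: "All other outcomes will be analysed using complete case data sets".

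SAP, Appendix A: weight is a row of Table A4 (imputed data). BMI and HOMA-IR are rows of Table A5, captioned "Exploratory outcome analyses for outcomes not used in the multiple imputation of the primary outcome, ie complete case analyses".

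SAP, Estimand Considerations: "For individuals who discontinued due to the diet a missing-not-at-random assumption will be made, assuming zero adherence after discontinuation". This governs the imputed analyses.

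SAP, R code, Analyses part: the outcome list has weight, fasting glucose and fasting insulin but neither BMI nor HOMA-IR.

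**The concern.** BMI is weight divided by the square of a fixed height. HOMA-IR, on its usual definition (the SAP does not spell one out), is fasting glucose times fasting insulin over a constant. Once the components are imputed, both are known in every imputed data set. The reason implied by the Table A5 caption, that an outcome had no part in the imputation, suits CGM, sleep or gut peptides. It does not suit two outcomes built entirely from imputed variables and height.

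Under the rule as written, weight and BMI, in effect one measurement on two scales, appear in neighbouring tables for different sets of people and under different missing-data assumptions. HOMA-IR likewise has a different analysis set from its two components in Table A1. A reader who sees the headline effects disagree could not tell whether the cause is physiology or the handling of drop-outs.

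**Working it through.** **Inputs from the SAP (Pre-planned Sample size; Error Control).** N = 114, 38 per group; SD of log AUC 0.152; pre-post correlation 0.85; difference 0.06; alpha 0.027 two-sided; drop-out below 10%. No planning figure is given for BMI or HOMA-IR.

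**Step 1: the SAP's own figure.** The ANCOVA SD is 0.152 × √(1 − 0.85²) = 0.080. With 38 × 0.9 = 34.2 per group, power is 81.3% by the normal approximation and 80.2% by the noncentral t. The stated power of over 80% reproduces. Only the drop-out limit is used below, and primary power does not depend on this point.

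**Step 2: how many people are affected.** 114 × 0.10 = 11.4 in total and 38 × 0.10 = 3.8 per arm. At the planning limit about 11 people, roughly 4 per arm, would be in the analyses of weight, fasting glucose and fasting insulin but not in those of BMI and HOMA-IR.

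**Step 3: how the derived outcomes follow from the components.**
- log BMI = log weight − 2 × log height. With height fixed, each person's change in log BMI equals the change in log weight.
- log HOMA-IR = log fasting glucose + log fasting insulin + constant. Each person's change is the sum of the two component changes.

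A simulation of 114 people with no treatment effect illustrates the first identity. With the same people and the same covariates, the two log-weight and log-BMI treatment effects were identical (−0.00036 and 0.00571). With each outcome adjusted for its own baseline, BMI gave −0.00065 and 0.00549, a small residual difference. On 104 complete cases, with people removed at random, BMI gave 0.00233 and 0.00580.

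**Step 4: the size of the mismatch.** Let d be the missing share in an arm and g the completer mean change minus the mean change assigned to those missing. The complete-case mean exceeds the all-randomised mean by d × g in each arm. With the same g in both arms, the treatment contrasts differ by (d_T − d_C) × g, where T is a time-restricted arm and C the control.

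The SAP supplies neither d by arm nor g, so these values are assumptions. Sizes are in percentage points on the log scale:

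| d_T vs d_C | BMI, g = −4% to −8% | HOMA-IR, g = −15% to −30% |
|---|---|---|
| 10% vs 10% | 0 | 0 |
| 10% vs 5% | 0.2 to 0.4 | 0.75 to 1.5 |
| 15% vs 5%, or 10% vs 0% | 0.4 to 0.8 | 1.5 to 3.0 |

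For example, (0.10 − 0.05) × (−4%) = −0.2 points. With g negative and more missing data in the time-restricted arm, the complete-case contrast is the more favourable one for that arm.

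**Step 5: precision.** 1/√0.9 = 1.054. This compares 90% of participants with nobody missing. Imputation does not restore full information, so 5.4% is an upper bound on the gain in standard error.

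**The case against.** The SAP does not contradict itself. It states one rule, the captions of Tables A4 and A5 repeat it, and both outcomes lie outside the ordered testing procedure. That stands: this is an analysis choice that can be improved, not an error of text.

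A partial like-for-like comparison also exists. Table A3 gives complete-case results for fasting glucose and fasting insulin, against which HOMA-IR can be read. The complete-case block of the R code runs over an outcome list that includes weight, although Table A3 has no weight row. This softens the point. It leaves the headline estimates in Tables A1 and A4 on a different footing from those in Table A5.

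A reader might infer three stronger things that the document does not support:
- **That diet-related discontinuers are all excluded.** Complete case removes people without week-8 data, not people who stopped the diet. The SAP reports discontinuation of the intervention separately from study withdrawal. It also invites early discontinuers to an assessment with fasting bloods and body weight, labelled week 6, without saying how those data are used. How many are lost is unknown.
- **That the BMI and HOMA-IR effects are biased.** This needs missingness, or the completer/drop-out difference, to be unequal across arms. The SAP gives no figure for either.
- **That about 5% of precision is lost.** Someone who misses the whole week-8 visit lacks all week-8 predictors together, leaving baseline values and adherence. The regression already adjusts for sex, baseline fasting glucose and the outcome's own baseline, so imputation would recover little of the 5.4%.

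Finally, exact agreement should not be expected even on one data set. The SAP does not say that HOMA-IR or BMI is analysed on the log scale (the list of logged variables is not shown), and each outcome is adjusted for its own baseline.

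**Conclusion.** The point holds as a low-severity inconsistency in missing-data handling. Two exploratory outcomes that are fixed functions of imputed variables are analysed in a different set of people, and without the zero-adherence assumption that applies to their components. At most about 11 of 114 participants are concerned if drop-out stays within the planning limit.

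The resulting difference is nil when missingness and the completer/drop-out difference are equal across arms. The figures of 0.2 to 0.8 points for BMI and 0.75 to 3 points for HOMA-IR illustrate assumed imbalances and are not estimates for this trial. No confirmatory conclusion, error rate or power figure changes. The case for change rests on consistency with the components and with the SAP's own handling of the three-meal mean AUC, not on precision or demonstrated bias.

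**What to change.** Derive BMI (from imputed weight and baseline height) and HOMA-IR (from imputed fasting glucose and fasting insulin, with the formula stated) at both visits within each of the 100 imputed data sets. Pool with Rubin's rules and move both rows from Table A5 to Table A4. Amend the Exploratory Outcomes sentence so that outcomes computed wholly from imputed variables and fixed baseline measures use the imputed data. State whether each is analysed on the log scale. Keep the complete-case results as a sensitivity analysis.

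The cost is small but not nil. Height is not among the listed imputation variables and must be merged in; since BMI is an eligibility criterion, it should be available from screening. Two derived variables and an edited outcome list complete the code change. The change removes the mismatch in population and missing-data assumption. It does not remove the small difference that comes from adjusting each outcome for its own baseline.

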Hypothesis testing framework: All analyses are to test for superiority of eCR and dCR over CR.

Analyses: No interim analyses are planned. The analysis of the primary outcome will be conducted after the final subject has completed their 8 week assessment and the blood samples assessed for glucose concentrations.

Error Control: There are two primary comparisons, eCR vs CR and dCR vs CR with a common control and thereby use a Dunnett multi-test adjustment that controls the familywise error rate at 0.05 (two-sided) when each pairwise test uses an alpha of 0.027 (two-sided).

There are four secondary efficacy outcomes that will be tested to support a confirmatory finding: (i) PP insulin AUC, (ii) fasting insulin, (iii) fasting glucose, and (iv) HbA1c. An ordered testing procedure with per comparison (eCR vs CR and dCR vs CR) will be applied testing these four secondary outcomes in the order listed here, testing each subsequent outcome only if the previous outcome (and primary outcome) rejected the null. This procedure is applied separately for each comparison: eCR vs CR and dCR vs CR. The same pairwise alpha level, 0.027 (two sided), as the primary outcome will be applied to ensure that the familywise error rate is controlled at 0.05 (two-sided).

Standard multiplicity unadjusted 95% confidence intervals will be reported for all comparisons.

Covariate adjustment: All comparisons of treatment effect will include adjustment for...

1. The outcome variable's baseline assessment if appropriate,
2. Stratification factors (sex and baseline fasting plasma glucose as a continuous variable)

Sensitivity Analyses: A best-worst case sensitivity analysis will be performed for the analysis of the primary outcome and secondary efficacy outcomes.

- For all individuals missing the week 8 assessment in the CR (control) group the outcome will be imputed assuming missing-at-random. In other words, as if each individual's mean adherence was continued, or the cohort's mean adherence if no adherence data is available for an individual.
- For individuals missing the week 8 assessment in the eCR and dCR groups their outcome, a missing-not-at-random assumption will be applied by assuming zero adherence and outcomes imputed thereafter, i.e., assuming missing-at-random conditional on zero subsequent adherence.
- These assumptions will be made irrespective of the stated reason for diet discontinuation.

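### The adverse event summaries drop repeat episodes, so a difference between arms in how often an event recurs cannot be seen; add event counts beside the maximum-grade person count

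*SAP*

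**What the plan says.** The Safety Outcomes section of the SAP plans two sets of summaries: "Summaries, for all adverse events and for those events believed to be related to the intervention, will be reported". For both it sets one counting rule: "if an individual has experienced the adverse event on multiple occasions, only the event with the maximum grade will be reported". The rule works within an event type. A person with two different events appears under each of them, once per event, at the worst grade reached.

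The comparison between arms is a Fisher test, run for any event that four or more people have had. Its purpose is given as "comparing the rates of occurrence (irrespective of grade) between the two intervention groups". It is a test on numbers of people and is not adjusted for multiple testing.

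No other part of the SAP plans a count of episodes or of people with recurrence. Tables A1 to A5 in Appendix A cover efficacy and exploratory outcomes only. Under Descriptive Statistics the SAP does plan an account of discontinuation, in which "the week and reason for discontinuation will be reported".

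**The concern.** The intervention is an eating pattern followed every day for eight weeks. The SAP lists no expected adverse events. It is an inference, though a reasonable one, that some complaints under such a regimen could come back in the same person. For events of that kind, the number of people ever affected is only part of the picture; how often they are affected is the other part.

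Under the stated rule, one episode and an episode every week produce the same entry. A time-restricted arm could differ from control in recurrence while having the same number of people affected, and both the table and the test would show no difference. The section speaks of rates, but what is compared is the proportion of people with at least one occurrence. A reader of the trial report could not recover the missing information.

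**Working it through.** The SAP states no safety figure, so there is none to reproduce. The check shows what the planned table and test can and cannot distinguish.

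**Inputs from the SAP**
- 38 participants per arm (Pre-planned Sample size).
- An eight-week period; the final analysis comes "after the final subject has completed their 8 week assessment" (Analyses).
- One record per person per event type, at maximum grade (Safety Outcomes).
- A Fisher exact test on people once at least four have the event (Safety Outcomes).

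**Assumed, not in the SAP:** the number of people affected and the number of episodes per affected person.

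**Illustration 1: 5 people affected in each of two arms**

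| | Arm X | Arm Y |
|---|---|---|
| Episodes per affected person (assumed) | 1 | 8 (weekly) |
| People affected, as the SAP would report | 5/38 = 13.2% | 5/38 = 13.2% |
| Total events, not reported | 5 × 1 = 5 | 5 × 8 = 40 |
| People with more than one event, not reported | 0 | 5 |

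Ten people have the event, so the threshold of four is met and the test is run. The two arms give identical counts of people, so it cannot show a difference. The ratio of events is 40/5 = 8.

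**Illustration 2: 8 people affected in each arm**

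The planned display is 8/38 = 21% in both arms, with Fisher p = 1.00. The result is the same whether the arms had 8 and 8, 8 and 24, or 8 and 56 episodes. Over 38 × 8 = 304 participant-weeks of full follow-up, 8, 24 and 56 episodes are 0.026, 0.079 and 0.184 per participant-week. The reported result does not change across a threefold or sevenfold difference.

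The episode numbers are constructed, but the loss they show follows from the rule itself. At any event rate, the planned output depends only on which people were affected and their worst grade.

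**Are the data available?** Choosing the maximum grade over several occurrences requires the individual occurrences and their grades to be recorded. The SAP does not say outright that every episode is logged, so this is an inference from the rule.

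**The case against.** The strongest reply is that this is a standard summary. Counting each person once per event at maximum grade is common practice. It also fits the Fisher test, which needs independent people as its units. Nothing in the section is contradictory, the SAP does not claim that recurrent low-grade events are the expected pattern, and the 5-against-40 contrast is an extreme chosen for clarity. All of this stands. It means that the rule should be kept and that the size of the problem in this trial is unknown. It does not answer the point that the rule, as written, leaves repeat occurrences out of the report altogether.

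Two stronger readings are tempting and should be resisted.

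A reader might take the rule to mean one worst event per person overall. The wording applies it within each adverse event, so different events in one person are all kept.

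A reader might also infer that the rule makes an arm with more early stoppers look safer. The SAP does not support that, for four reasons:
- The maximum-grade rule has no link to early stopping. Any such effect would come from unequal observation, and only if adverse event collection ends when the diet stops. The SAP does not say so. In the estimand table, early stoppers are to "be invited to attend the week 6 assessment for fasting bloods and body weight only", which limits the assessments but sets no end to adverse event collection.
- Someone who stops because of an adverse event has already been counted.
- The number, week and reason of discontinuation are to be reported, so intolerance in one arm would be visible.
- The effect would be small even in the unfavourable case. Take p = 5/38, four people stopping at week 2, a constant weekly hazard λ = −ln(1 − p)/8 = 0.0176, and no later collection. The expected number affected is 34 × 0.1316 + 4 × (1 − exp(−2λ)) = 4.47 + 0.14 = 4.6, against 5.0. That is less than half a person.

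A separate matter in the same paragraph is that the test is described as comparing two intervention groups in a three-arm trial. That is not part of this point and lends it no weight.

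**Conclusion.** The point holds in a limited form. The SAP confines its adverse event reporting to people affected at maximum grade, and a difference between arms in recurrence over the eight weeks would not appear in the table or the test. In the illustration an eightfold difference in events (5 against 40) shows as 13% in both arms. That size rests entirely on assumed episode numbers; the loss of information does not depend on them.

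The person-level count and the test are sound. No claim about bias from early stopping is warranted. This is a minor reporting improvement, between optional and advisable, and it has no bearing on the primary analysis.

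**What to change.** Keep the maximum-grade count of people and the person-level test. In Safety Outcomes, add a sentence such as: *For each adverse event term and each arm, for all events and for related events, the total number of events and the number of participants with more than one event will be reported alongside the number of participants affected by maximum grade.*

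Participant-weeks are not required. If observation time is shown at all, it should run to the end of adverse event collection, not to the week in which the diet was stopped. Under Descriptive Statistics the SAP treats stopping the intervention and withdrawing from the study as separate things. Using the week of stopping the diet could shorten the denominator while later events were still counted.

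The cost is one sentence and two columns in the safety table, with no new test and no change to the sample size. If repeat occurrences are recorded, as the rule implies, no new data are needed. The only downside is a slightly longer table.
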